8.3 EXPLORATORY ENDPOINT ANALYSES

The exploratory efficacy outcome measures for this study are the following:

- cCR rate
- Relapse Free Survival (RFS)
- Progression Free Survival (PFS)
- Duration of Responses (CR, cCR)
- Time to CR
- CR within 6 cycles

Additional to the exploratory endpoints a summary table will be generated for the best response reached during study course by each subject.

Quality of life is described in section 8.4.

Composite Complete Remission (cCR) rate

Composite complete remission (cCR) rate is defined as the proportion of patients who achieve either a disease response of CR, CRi (Morphologic Complete Remission with incomplete blood count recovery; see Appendix F of the protocol for further information) or MLFS (Morphologic Leukemia Free State; see Appendix F of the protocol for further information) (ie, $cCR = CR + CRi + MLFS$) within the study period, according to the IWG Criteria (Appendix F of the protocol). Absence of interceding therapies is requested for considering the response in the analysis.

Composite CR rate will be analyzed on the ITT and the EE-1 sets. Composite CR rate will be analyzed using the same methods as those used for the CR rate analysis, limiting to the stratified analysis. Patients for whom no efficacy assessment is available will be analyzed as not having cCR when considering the ITT set.

Relapse-free Survival (RFS)

RFS is defined as the time from the date of achievement of CR or CRi until the date of relapse (progression) or death from any cause, whichever occurs first.

The analysis set will be the ITT set limited to patients who achieve a CR/CRi in absence of interceding therapies.

Censoring rules are:

- Time to relapse (progression) will be censored at the date of the last assessment of patient status that excluded relapse (progression). Current disease status field in the CRF page of long-term follow-up visits is to be considered as adequate information.
- In case of no disease assessments after CR, censoring will be at the date of CR/CRi.

RFS will be analyzed using the same methods as those used for OS (Kaplan Meier estimates and stratified log-rank test).

In addition, the influence of additional censoring criteria on RFS in the two treatment groups will be analyzed, namely censoring at the start date of a new cancer therapy instead of censoring at the date of the last assessment in the study.

Progression-Free Survival (PFS)

PFS is defined as the time from the date of randomization until the date of relapse (progression) or death from any cause, whichever occurs first.

The analysis set will be the ITT set.

Censoring rules are:

- Time to relapse (progression) will be censored at the date of the last assessment of patient status that excluded relapse (progression). Current disease status field in the CRF page of long-term follow-up visits is to be considered as adequate information.
- In case of no disease assessments, censoring will be at the date of randomization.

PFS will be analyzed using the same methods as those used for OS (Kaplan Meier estimates and stratified log-rank test).

In addition, the influence of additional censoring criteria on PFS in the two treatment groups will be analyzed, namely censoring at the start date of a new cancer therapy instead of censoring at the date of the last assessment in the study.

Duration of Morphologic Complete Remission (CR)

Duration of CR is defined as the time from the date of achievement of CR until the date of relapse (progression). Kaplan-Meier methods will be used to estimate duration of response in each treatment group. Duration of CR will be analyzed using the same methods as those used for OS (Kaplan Meier estimates and stratified log-rank test).

Censoring rules will include the following:

- Time will be censored at the date of the last adequate assessment of patient status that excluded relapse (progression). In case of no disease assessments after CR, censoring will be at the date of CR.
- Time will be censored at the start of interceding therapies

The analysis set will be the ITT set limited to patients who achieve a CR in absence of interceding therapies.

Duration of Composite Complete Remission (cCR)

Duration of cCR response is defined as the time from the date of achievement of either CR, CRi or MLFS until the date of relapse (progression) and will be analyzed as the duration of CR response.

Censoring rules will include the following:

- Time will be censored at the date of the last assessment of patient status excluding relapse. In case of no disease assessments after cCR, censoring will be at the date of cCR.
- Time will be censored at the start of interceding therapies

The analysis set will be the ITT set limited to patients who achieve a cCR in absence of interceding therapies.

Time to Morphologic Complete Remission (CR)

Time to CR is defined as the time from the date of randomization until the date of first CR in the absence of interceding therapies.

The analysis set will be the ITT set.

Time to CR will be censored at the date of the last assessment of patient status excluding CR in the case no CR occurred by time of analysis. In case of interceding therapies, PD or death, time to CR will be censored to the start date of the interceding therapy, PD assessment date or death date respectively. Cumulative Incidence Function (CIF) will be computed as 1-Kaplan Meier curve and treatment groups will be compared by the stratified (cytogenetic risk and ECOG PS at randomization) log-rank test.

Morphologic Complete Remission (CR) within 6 cycles rate

Morphologic complete remission (CR) within the first 6 cycles rate is defined as the proportion of patients who achieve CR in the absence of interceding therapies within 6 treatment cycles (i.e. during treatment phase up to Day 1 of Cycle 7 included). Analysis will be performed in the ITT set.

CR within 6 cycles rate will be analyzed using the same methods as those used for the CR rate analysis, limited to the stratified analysis. Patients for whom no efficacy assessment is available will be analyzed as not having CR.

Best Response

A summary table including the best response obtained during study course will also be presented (number of patients and related percentage).

For each patient the response assessment will be classified as best response using the following criteria:

- Morphologic Complete Remission (CR) as highest level,
 - Cytogenetic Complete Remission (CRc)

followed by

- Morphologic complete remission with incomplete blood count recovery (CRi),
- Morphologic leukemia free state (MLFS)
- Partial Remission (PR),
- Stable disease (SD)
- Progression

and the two summary response classifications:

- Composite Complete Response (patients with at least MLFS)
- Overall Response (patients with CR or CRi or MLFS or PR)

The criteria used for the single responses will be adequately used also for the two summary classifications.

The analysis sets will be the ITT and the EE-1 set. The corresponding ITT-2 and EE-2 sets will be the basis for the analysis of CRc.

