7 DISCONTINUATION FROM STUDY TREATMENT PHASE OF THE STUDY

7.1 Patient Treatment Discontinuation

If patients experience any of the following, then they must discontinue from the study treatment phase of the study:

- Documented disease progression or relapse after CR by the International Working Group (IWG) criteria ([Appendix F](#)).
- Lack of clinical benefit. Clinical responses may require at least 6 courses of study treatment. Therefore, discussion with the Medical Monitor is recommended prior to discontinuation of a patient on the basis of lack of clinical benefit.
- Irreversible or intolerable toxicity or abnormal and clinically significant laboratory findings that cannot be managed with study treatment dose reduction or interruption.
- A patient's request to discontinue treatment for any reason. If a patient requests discontinuation from study treatment due to an AE, the primary reason for discontinuation should be the adverse event.
- Non-compliance with study treatment or study-related assessments that compromise the proper evaluation of the patient's safety
- Lost to follow-up.
- Sponsor decision: The Sponsor reserves the right to discontinue the study at any time for either clinical or administrative reasons. This decision will impact patients in the treatment and in the Long-term Follow-up phases of the study.
- Pregnancy.

Upon study treatment discontinuation, assessments of the End of Treatment Visit must be completed (refer to Section [5.1.14](#)). Discontinued patients will enter the Long-term Follow-up phase of the study (refer to Section [5.2](#)). Every attempt must be made to contact the patient prior to assigning the patient a lost to follow-up status. For patients who are lost to follow-up, no Long-term Follow-up is expected.

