In addition, possible analyses based on other censoring criteria (e.g. censoring at the date of start of a new therapy) will be specified in the SAP. The analysis set will be the ITT set limiting to patients who achieve a cCR in absence of interceding therapies, including salvage treatments and HSCT.

9.7.3.6 *Time to CR*

Time to CR is defined as the time from the date of randomization until the date of CR in the absence of interceding therapies, including salvage treatments and HSCT. The analysis set will be the ITT set.

Time to CR will be censored at the date of the last assessment of patient status excluding CR in the case no CR occurred by time of analysis. In case of interceding therapies, PD or death, time to CR will be censored to the new AML treatment start date, PD assessment date or death date, respectively. Cumulative Incidence Function (CIF) will be computed as 1-Kaplan Meier curve and treatment groups will be compared by the log-rank test.

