5.5 SIGNIFICANCE LEVEL

The overall significance level for the primary efficacy endpoint is 0.025 (one sided). As an interim analysis according to the O'Brien Fleming function for superiority and the Gamma family function (with $\gamma=-5.4695$ for non-binding futility) will be done after 260 events (2/3 of the total number of events), the respective significance levels are 0.00605 for the interim and 0.02314 for the final analysis. These significance levels will be re-computed at time of analysis based on the real fraction of information available.

Calculations of significance levels and related thresholds were performed by means of SAS PROC SEQDESIGN.

The following table shows probabilities to stop at interim analysis for futility or superiority with the null and alternative hypotheses for the primary endpoint:

Table 1 Probability to stop at Interim Analysis HA as Median OS	10 months	14 months
Gamma spending function $\gamma=-5.4695$ for futility	0.70094	0.01442
O'Brien Fleming for superiority	0.00605	0.58059

The following table shows probabilities of significant results for the first secondary endpoint, according to the chosen hierarchical procedure and assuming no need to consider the correction for multiplicity as 100% of information would be collected (which was the assumption at time of SAP V1). The reference alternative hypothesis is that the difference between treatments in the CR rate is 0.13 (having 0.20 as the rate for the placebo group). Probabilities are corrected by unconditional probability of significant results for the primary endpoint as conditional probability assumes the correlation between endpoints to be known. The obtained results are conservative and represent the lower probability bound assuming no correlation.

Table 2		
Secondary endpoint(s)		
Assumption: 100% information for secondary endpoint at interim analysis is available		
probability of significant results	0.13 rate difference	
	Independent from primary endpoint (i.e. as it was the only endpoint in the study)	Hierarchical procedure *
at Interim Analysis	0.91	0.55
Overall	0.91	0.82

* rounded power for the primary endpoint is 0.90 overall and 0.60 at interim analysis, respectively (median OS = 14 months vs. 10 months)

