8.2 SECONDARY ENDPOINT ANALYSES

The secondary efficacy outcome measures for this study are the following (the order is relevant to the sequence procedure for testing endpoints):

- Morphologic Complete Remission (CR) rate

- Transfusion independence
- CR_{M RD}- rate
- CR_c rate

A group-sequential procedure will be applied as described in section 5.5.

Morphologic Complete Remission (CR) rate

The rate of CR is defined as the proportion of patients who achieve a morphologic CR according to the IWG response criteria (Appendix F of the protocol) in the absence of interceding therapies, including salvage treatments and hematopoietic stem cell transplantation (HSCT), within the study period. Interceding therapies, salvage treatments, as well as HSCT are collected in the “New AML Treatment” eCRF page and in the concomitant medication page (if started before and continued into the treatment period or started during treatment period). The proportions in the two treatment groups will be compared using the Cochran-Mantel-Haenszel test stratified for cytogenetic risk and ECOG PS (values stated at randomization).

The level of significance to be adopted is described in Section 5.5.

In addition, the two-sided 95% CI for the difference between the responder proportions in the two treatment groups will be provided, using the stratified Newcombe method.

The analysis will be primarily performed in the ITT set (patients for whom no efficacy assessment is available will be analyzed as not having CR) and then in the EE-1 set.

Unstratified analysis will be done for sensitivity purpose by means of likelihood ratio Chi square test.

Logistic regression models will be set up including also demographic characteristics (especially the AML history variables as described in section 7.2) and factors described in section 5.3 as covariates to explore the influence of these variables on CR rate (likelihood ratio test to compare different models and Wald test to evaluate covariates within a model).

Transfusion Independence

For the evaluation of transfusion independence (which is defined as achieving eight weeks or longer with neither red blood cell nor platelet transfusions during the study period), the following transfusions are regarded as “relevant” transfusions:

- Red Blood Cell (RBC) transfusions
- Platelet (PLT) infusions
- Whole Blood infusions

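### Time to CR (exploratory): calling 1−Kaplan-Meier a cumulative incidence function, with death, PD and new AML therapy censored, overstates the probability of CR

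*SAP*

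**What the plan says.** SAP 8.3 measures time to CR from randomization to first CR in the ITT set, counting only a CR reached without interceding therapy. Patients who have not reached CR by the analysis are censored at their last assessment. For the other outcomes the rule is: "time to CR will be censored to the start date of the interceding therapy, PD assessment date or death date respectively". The next sentence reads: "Cumulative Incidence Function (CIF) will be computed as 1-Kaplan Meier curve". Arms are compared by a log-rank test stratified by the randomization factors.

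Protocol 9.7.3.6 gives the same censoring and the same estimator: "Cumulative Incidence Function (CIF) will be computed as 1-Kaplan Meier curve and treatment groups will be compared by the log-rank test".

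Three other places bear on the point:

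- Protocol 7.1 lists documented disease progression among its mandatory reasons for leaving treatment: "If patients experience any of the following, then they must discontinue from the study treatment phase of the study".
- For the CR rate, the first secondary endpoint, SAP 8.2 uses the ITT denominator, and "patients for whom no efficacy assessment is available will be analyzed as not having CR". CR within 6 cycles is handled the same way in SAP 8.3.
- SAP 8.3 lists time to CR as exploratory, outside the fixed sequence in SAP 5.4.

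Neither document plans a competing-risks estimate for this endpoint. The summary table in SAP 13 has one line for it, with no sensitivity analysis.

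**The concern.** Kaplan-Meier treats a censored patient as someone who could still have the event later, at the same rate as those still under observation. That is reasonable for a patient cut off by the data cut. It is not reasonable here. A dead patient cannot reach CR. A CR after interceding therapy is not counted, by the endpoint's definition. A patient with PD must stop study treatment. The estimator therefore credits patients who can no longer respond with remissions they will not have.

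The label makes it worse. A reader takes a curve called a cumulative incidence function to be the proportion of randomized patients who have reached CR by each time, and will compare its plateau with the ITT CR rate. The two displays would give different CR probabilities for the same patients. The gap between arms read off the curves can also be wrong in either direction, because the excess depends on each arm's rate of competing events. The trial is designed to detect a difference between arms in one of those rates, death.

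**Working it through.** **Inputs from the documents**

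- CR rates: placebo 0.20, pracinostat 0.20 + 0.13 = 0.33 (SAP 5.5).
- Median OS: 10 and 14 months (SAP 3.3). If exponential, the monthly death hazards are ln 2/10 = 0.0693 and ln 2/14 = 0.0495.
- 500 patients, 1:1, so 250 per arm (Protocol 9.11; SAP 3.1).

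**Assumptions not in the documents:** constant hazards; a time T by which the planning CR rates are reached; and any hazard of PD or new therapy beyond death. The documents give no rate for either.

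**The plan's own figure.** No number is given for the time-to-CR curve. The nearest is the power of 0.91 for the CR rate in SAP 5.5, Table 2. Two proportions of 0.20 and 0.33, 250 per arm, one-sided 0.025, give 0.911, so the planning rates are read correctly.

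**Formulas.** With CR hazard h and competing hazard c:

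- true cumulative incidence: CIF(T) = h/(h+c) × [1 − exp(−(h+c)T)]
- the planned curve: 1−KM(T) = 1 − exp(−hT)

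The second is the first with c set to zero, so it can never be the smaller. For each arm, h is solved so that CIF(T) equals 0.20 or 0.33, and the planned curve is read at the same T.

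**Worked case, T = 12 months, death only**

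- Placebo: c = 0.0693, h = 0.0283. Check: 0.0283/0.0976 × [1 − exp(−1.171)] = 0.290 × 0.690 = 0.200. Planned curve: 1 − exp(−0.340) = 0.288.
- Pracinostat: c = 0.0495, h = 0.0463. Check: 0.0463/0.0958 × [1 − exp(−1.149)] = 0.483 × 0.683 = 0.330. Planned curve: 1 − exp(−0.555) = 0.426.

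In this case 49% of placebo and 35% of pracinostat patients die before any CR within 12 months.

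**Adding a PD/new-therapy hazard, T = 12 months** (true values 0.20/0.33, difference 0.130)

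| Extra monthly hazard, placebo/pracinostat | Total c | 1−KM | Excess | Arm difference |
|---|---|---|---|---|
| 0/0 | 0.0693/0.0495 | 0.288/0.426 | 0.088/0.096 | 0.138 |
| 0.05/0.05 | 0.1193/0.0995 | 0.358/0.527 | 0.158/0.197 | 0.169 |
| 0.05/0.025 | 0.1193/0.0745 | 0.358/0.476 | 0.158/0.146 | 0.119 |
| 0.08/0.04 | 0.1493/0.0895 | 0.401/0.507 | 0.201/0.177 | 0.106 |

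**Other horizons, death only:** 0.242/0.377 at 6 months (excess 0.042/0.047) and 0.385/0.526 at 24 months.

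**Simulated checks, death only, 12 months**

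- 400,000 patients per arm: 1−KM 0.288/0.425 against observed CR proportions of 0.200/0.329.
- CR detected only at even-cycle marrow assessments, 200,000 per arm: 1−KM 0.269 against 0.180 on placebo, and 0.400 against 0.301 on pracinostat.
- CR possible only in months 2 to 8: 1−KM 0.278/0.416.

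**Effect on the arm comparison, death only, 12 months.** If both arms had a CR hazard of 0.03 per month, the planned curves would coincide at 0.302, while the true probabilities would be 0.210 and 0.232. If both arms truly had 0.25, the planned curves would show 0.357 on placebo and 0.325 on pracinostat.

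**The case against.** The strongest case is that little depends on this curve. Time to CR is exploratory. The log-rank test with these events censored is a valid comparison of cause-specific CR hazards. The probability of CR is already estimated soundly as an ITT proportion, both overall and within 6 cycles. All of this stands, and it limits the point to the curve, its label and any probability read from it.

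The size can also be challenged:

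- The planning CR rates carry no time horizon, so 12 months is a choice. Phase II points to something shorter for many patients: 21 of 50 reached CR (Protocol 1.3) and 6 needed more than 6 cycles (Protocol 3.1), so 15 of 21 responded within 6 × 28 = 168 days, about 5.5 months. At 6 months with death alone the excess is only 0.04 to 0.05. That lower figure belongs in the range.
- With death as the only competing event the arm difference barely moves: 0.135 at 6 months and 0.138 at 12, against 0.130. The wider spread of 0.106 to 0.169 comes from PD and new-therapy hazards the documents do not supply. Equally, the documents give no basis for taking those hazards as zero.
- Part of any mismatch with the ITT rate comes from ordinary censoring at the last assessment. A correct competing-risks curve could also sit somewhat above the crude proportion, so the fix narrows the gap and may not close it.

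Finally, strict excess needs at least one competing event before a later CR in that arm. With a 10-month control median and marrow assessments every second cycle, that condition will in practice be met. These points bear on size, not on whether the estimator is wrong.

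**Conclusion.** The concern holds. As written, both documents label as a cumulative incidence function something that is not one, and its bias is upward. On the planning CR rates and OS medians, with constant hazards, death alone adds 0.04 to 0.05 per arm at 6 months and 0.09 to 0.10 at 12 months. With the PD and new-therapy hazards assumed above, the 12-month excess is 0.15 to 0.20 per arm, and the arm difference lies between 0.106 and 0.169 against a true 0.130. Those figures rest on the assumed horizon, constant hazards and extra hazards; the direction does not. The type I error rate, power, fixed testing sequence and primary conclusion are unaffected. It should be corrected because the error is clear and the correction is simple.

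**What to change.** In SAP 8.3, replace the 1−Kaplan-Meier sentence with one stating that the cumulative incidence of CR is estimated by the Aalen-Johansen method, with death, PD and interceding therapy as competing events. Patients without CR or any of these events remain censored at their last assessment. Keep the stratified log-rank test, described as a comparison of cause-specific CR hazards; Gray's test is optional. Make the same correction in Protocol 9.7.3.6. If the protocol is not being amended, SAP 11 already records changes the protocol does not carry. At the very least, the 1−Kaplan-Meier curve should not be called a cumulative incidence function.

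The cost is one sentence in each document and an event code in PROC LIFETEST, in the SAS 9.4 already specified in SAP 5.1. The existing censoring rule already requires the death, PD and new-therapy dates, so no new data are needed.

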8.4 QUALITY OF LIFE

Quality of life will be evaluated using the EORTC QLQ-C30 questionnaire.

The following scores will be analyzed by treatment group presenting absolute score value and change from baseline for the different visits where the questionnaire was to be filled in:

- Global Health Status / QoL (questions 29, 30)
- Functional Scale “Physical Functioning” (questions 1 to 5)
- Functional Scale “Role Functioning” (questions 6,7)
- Symptom Scale / Item “Fatigue” (questions 10, 12, 18)
- Symptom Scale / Item “Nausea and Vomiting” (questions 14, 15)
- Symptom Scale / Item “Appetite Loss” (question 13)

All other functional and symptom scale scores will be computed and listed. These are

- Functional Scale “Cognitive Functioning” (questions 20, 25)
- Functional Scale “Emotional Functioning” (questions 21 to 24)
- Functional Scale “Social Functioning” (questions 26, 27)
- Symptom Scale / Item “Pain” (questions 9, 19)
- Symptom Scale / Item “Dyspnoea” (question 8)
- Symptom Scale / Item “Insomnia” (question 11)
- Symptom Scale / Item “Constipation” (question 16)
- Symptom Scale / Item “Diarrhoea” (question 17)
- Symptom Scale / Item “Financial Difficulties” (question 28).

The analysis set will be the ITT set.

